#### 10.1.1 Definition of intensity

The clinical intensity of an AE will be classified as:

- *Mild:* Signs and symptoms that can be easily tolerated. Symptoms can be ignored and disappear when the subject is distracted.
- *Moderate:* Signs and symptoms that cause discomfort and interfere with normal functioning, but are tolerable. They cannot be ignored and do not disappear when the subject is distracted.
- *Severe:* Signs and symptoms that affect usual daily activity and incapacitate the subject, thereby interrupting his/her daily activities.

The definitions above are difficult to apply for some data (e.g., clinically relevant laboratory values that are documented and evaluated on the eCRF AE report page). In such situations, the investigator should make a judgment based on personal experience.

## 10.1.2 Definition of causal relationship with investigational product

An AE is considered to be "related" to IP if a causal relationship between the IP and an AE is at least a reasonable possibility (i.e., the relationship cannot be ruled out).

The expression "reasonable causal relationship" is meant to convey that there are facts (evidence) or arguments to suggest a causal relationship (ICH E2A guideline). Otherwise, the relationship should be considered as "not related."

### 10.1.3 Categories of actions taken and outcome

Action taken with the IP:

- Drug withdrawn (no further study injections given).
- Dose reduced (at the next injection possible i.e. at V10a [injection cycle 3] or V14a [injection cycle 4] only, due to weight loss or AEs).
- Dose increased (at next injection visit i.e. at V10a or V14a only, according to weight gain of subject).
- Dose not changed.
- Unknown.
- Not applicable.
- Drug withdrawn temporarily (further study injections delayed).

The reportable outcomes and/or sequelae of an AE are as follows:

- Recovered/resolved.
- Recovering/resolving.
- Not recovered / not resolved.
- Recovered / resolved with sequelae.
- Fatal.
- Unknown.

If there is more than one AE, only the AE leading to death will be attributed with a "fatal" outcome.

#### 10.2 Definition of a serious adverse event

An SAE is any untoward medical occurrence, at any dose, that:

• Results in death.

- Is life-threatening.
- Requires inpatient hospitalization, or prolongation of existing hospitalization.
- Results in persistent or significant disability/incapacity.
- Is a congenital anomaly/birth defect.
- Consists of any other medically important condition.

For this study the following may be considered important medical conditions: suicidal ideation (a response of "yes" to questions 4 or 5) or any suicidal behavior as indicated by the C-SSRS and confirmed by the Investigator or when reported based on other information by the Investigator.

In case of death, an autopsy report should be submitted (if available). The date and cause of death should be recorded.

Hospitalizations for elective treatments planned before screening and which are documented in the subject's source data are usually not regarded as SAEs.

All SAEs that occur during the study period, whether considered to be related to IP(s) or not, must be reported by telefax, telephone or e-mail within 24 hours of knowledge of the event. SAE report forms are provided in the ISF.

Although all information required for completion of an SAE report form may not be available within the specified time period, an initial report should be submitted if the following minimal information is available:

- An identifiable subject (number).
- A suspect product.
- An identifiable reporting source (investigator/study site identification).
- An event or outcome that can be identified as serious.

The report must be delivered to the report assessing site of the CRO listed below.

<sup>3 The term "life-threatening" in the definition of "serious" refers to an event in which the subject was at risk of death at the time of the event; it does not refer to an event that hypothetically might have caused death if it were more severe.

<sup>4 According to ICH E2A, CPMP/ICH/377/95: "Medical and scientific judgment should be exercised in deciding whether expedited reporting is appropriate in other situations, such as important medical events that may not be immediately life-threatening or result in death or hospitalization but may jeopardize the patient/subject or may require intervention to prevent one of the other outcomes listed in the definition above. These should also usually be considered serious. Examples of such events are intensive treatment in an emergency room or at home for allergic bronchospasm; blood dyscrasias or convulsions that do not result in hospitalization; or development of drug dependency or drug abuse."

The address for SAE reporting is:

The investigator must supply further supporting information within 3 days of knowledge of the SAE, and a detailed SAE description is an integral part of this supporting information. Follow-up reports should be sent without delay to the CRO as an SAE report form (marked as a "follow-up" report) and accompanied by appropriate supporting documentation (e.g., hospital reports). The SAE has to be followed up until the SAE is resolved/recovered or a plausible explanation is available. These SAEs will be followedup only in the Corporate Product Safety database after final SAE reconciliation is completed.

SAEs occurring after the end of the observational period need only be reported if the investigator considers the event to be related to the IP. These reports generally will not be entered into the study database.

#### 10.3 Adverse events of special interest (alert terms)

All AEs of special interest (alert terms) that occur during the study period, whether considered to be related to IP(s) or not, must be reported by telephone, telefax, or secure e-mail within 24 hours of knowledge of the event (see contact details in Section 10.2.)

At each visit the investigator or a representative authorized by the investigator will ask actively the child/adolescent (if applicable) or his/her parent(s)/carer about the occurrence of AESIs.

For this study, the following AEs are defined as AESIs:

MedDRA Preferred Term (MedDRA version 15.1)						
Accommodation disorder	Eyelid ptosis	Peripheral nerve palsy				
Areflexia	Facial paresis	Peripheral paralysis				
Aspiration	Hemiparesis	Pelvic floor muscle weakness				
Botulism	Hypoglossal nerve paresis	Pneumonia aspiration				
Bradycardia	Hyporeflexia	Pupillary reflex impaired				
Bulbar palsy	Hypotonia	Quadriparesis				
Constipation	Ileus paralytic	Respiratory arrest				
Cranial nerve palsies, multiple	Monoparesis	Respiratory depression				
Cranial nerve paralysis	Muscular weakness	Respiratory failure				
Diaphragmatic paralysis	IIIrd nerve paresis	Speech disorder				
Diplopia	IVth nerve paresis	Trigeminal nerve paresis				
Dysarthria	VIIth nerve paralysis	Urinary retention				
Dysphagia	Paralysis	Vision blurred				
Dysphonia	Paralysis flaccid	Vocal cord paralysis				
Dyspnea	Paraparesis	Vocal cord paresis				
Extraocular muscle paresis	Paresis					
Eyelid function disorder	Paresis cranial nerve					

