# 7.4 Eligibility criteria for continued treatment in the extension period

Criteria for the transition to the extension period (V6/6a) and for continued treatment within the extension period (V10/10a and V14/14a) are listed below. (Note that the pairs of visits 6/6a, 10/10a and 14/14a will normally take place on the same respective day.)

If these eligibility criteria are not fulfilled at the end-of-cycle visit postponement of study treatment may take place at the beginning of the following injection cycle of the extension period. The re-injection visit can be postponed for up to a maximum of two weeks (but no longer than 18 weeks after the preceding treatment visit). For subjects who still do not fulfill the eligibility criteria at the revisit, study participation will be ended.

	Eligibility Criteria for Extension Treatment	Ratio- nale	Visits 6, 6a, 10, 10a, 14, 14a
1.	Clinical need for re-injection.	Ind	Х
2.	Absence of medically-relevant severe adverse events of special interest that are judged to have a causal relationship to the study treatment (indicative of toxin spread in the area of injection), especially respiratory arrest/distress/failure and dysphagia necessitating diet changes occurred during any period of the study.	Safety	Х
3.	No concomitant infection or inflammation in the head and neck region.	Safety	Х

Page 52 of 183

		Eligibility Criteria for Extension Treatment	Ratio- nale	Visits 6, 6a, 10, 10a, 14, 14a
4.	Neg fem	ative result of pregnancy test (testing only performed for ale with history of menarche, i.e. the first menstrual bleeding).	Safety	Х
5.	No :	significant risk of suicidality since last injection based on the Investigator's judgment, and	Safety	Х
	•	if appropriate, as indicated by a response of "no" to questions 4 or 5 in the suicidal ideation section of the C-SSRS		
	•	and no non suicidal self-injurious behavior		
	•	and no suicidal behavior.		

Definition of indication for continued study treatment [Ind]; administrative [Adm].

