## 7.5 Removal of subjects from treatment or assessment

## 7.5.1 Discontinuation of subject's study participation

In accordance with the Declaration of Helsinki and the informed consent form, the subject or his/her parent(s) may discontinue the subject's participation in the study at any time without any penalty or loss of benefits to which the subject is otherwise entitled (see Section 7.5.3). Both the premature withdrawal from the study and the reason(s) for this are to be recorded in the subject's file and the eCRF. The date and circumstances of the discontinuation should be stated.

Subjects are to be withdrawn from the study by the investigator at any time if any of the following occurs:

- Withdrawal of informed consent.
- Pregnancy (no further administration of NT 201, blood sampling, or any other interventional or invasive procedure will be performed).
- Any AE for which treatment continuation would constitute an unacceptably high risk for the subject.
- Any eligibility criteria for reinjection are not met within 18 weeks after the previous injection of IP in the respective injection cycle (MP or OLEX).

- AESIs of severe intensity that represent respiratory function disorders or swallowing disorders will trigger the premature termination of a subject without reexposition to IP. The terms for these severe AESIs are:
  - AESI terms related to respiratory function disorders are aspiration, diaphragmatic paralysis, dyspnoea, pneumonia aspiration, respiratory arrest, respiratory depression, and respiratory failure.
  - AESI terms related to swallowing disorders are bulbar palsy, multiple cranial nerve palsies, dysphagia, hypoglossal nerve paresis, cranial nerve paresis, cranial nerve paralysis.
- Positive report on suicidality of subject (C-SSRS answer "yes" to questions 4 or 5 or any suicidal behavior) or non-suicidal self-injurious behavior.

Deviations from this clinical study protocol, or conditions arising from the exclusion criteria as set out in Section 7.3, may (but will not necessarily) lead to the subject's withdrawal. All such conditions are to be properly documented. In such cases, the decision on whether or not to withdraw the subject will be made by the investigator in consultation with the sponsor, taking principally the safety of the subject into account.

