# 7.5.2 Premature termination or suspension of the study or a study site

The study or a study site can be terminated prematurely, or suspended, by the sponsor. Reasons for termination of the study or closure of a study site may include, but are not limited to, the following:

- Subject enrollment is unsatisfactory.
- The risks and benefits of continuing the study have been reassessed, and the risks outweigh any potential benefits.
- The incidence of AEs constitutes a potential health hazard to the subjects.

- New scientific data on NT 201 do not justify a continuation of the study.
- The investigator or study site exhibit serious and/or persistent non-adherence to the clinical study protocol, the Declaration of Helsinki, ICH–GCP, and/or applicable regulatory or clinical requirements.
- The sponsor decides to terminate the study at any time for any other reason (e.g. based on the recommendation of the DMC).
- AESIs of severe intensity that represent respiratory function disorders or swallowing disorders, that are deemed to be related to IP administration, and that last >1 week will trigger premature termination of the study. The threshold for premature study termination is set to at least five of the severe AESIs described above for the first 50 subjects injected. Once 50 or more subjects have been treated in this study the threshold is set to at least 10% of all treated subjects.
- AESI terms related to respiratory function disorders are aspiration, diaphragmatic paralysis, dyspnoea, pneumonia aspiration, respiratory arrest, respiratory depression, and respiratory failure.
- AESI terms related to swallowing disorders are bulbar palsy, multiple cranial nerve palsies, dysphagia, hypoglossal nerve paresis, cranial nerve paresis, cranial nerve paralysis.

Furthermore, the study (or the participation of a study site) may be ended prematurely if the regulatory authority or the IEC/IRB decides to terminate or suspend approval for the study, the study site, or the investigator.

If the study is prematurely terminated or suspended for any reason, the investigator must inform the subjects and/or their legally acceptable representatives and ensure appropriate follow-up treatment. Within the time-frames stipulated in the applicable regulations, the sponsor will promptly inform the investigators, study sites, IEC/IRB and regulatory authorities of the termination or suspension of the study, and will provide reasons for this action.

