#### 6.5.2 Secondary safety variables

- Occurrence of treatment emergent AESIs (TEAESIs) overall and by injection cycle.
- Occurrence of treatment emergent SAEs (TESAEs) overall and by injection cycle.
- Occurrence of TEAEs related to treatment as assessed by the investigator overall and by injection cycle.
- Occurrence of TEAEs leading to discontinuation overall and by injection cycle.

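### Section 7.4 treats severe, related respiratory distress as an AESI, but the closed AESI list in 10.3 and the lists that follow it omit the term

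*Protocol*

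**What the plan says.** **Re-injection (Protocol 7.4, criterion 2).** A further injection requires that no severe AESI with a causal link to treatment, of the kind that suggests toxin spread, has occurred. The criterion stresses certain events: "especially respiratory arrest/distress/failure and dysphagia necessitating diet changes occurred during any period of the study". As the sentence is built, respiratory distress is one of the examples of an AESI.

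**Definition (Protocol 10.3, Table 7).** AESIs are defined by a list: "For this study, the following AEs are defined as AESIs". The text after Table 7 adds only dry mouth that is severe, serious or irreversible. Each AESI, related or not, "must be reported by telephone, telefax, or secure e-mail within 24 hours of knowledge of the event".

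**Withdrawal (Protocol 7.5.1).** "AESIs of severe intensity that represent respiratory function disorders or swallowing disorders will trigger the premature termination of a subject without reexposition to IP". The respiratory terms are spelled out: "AESI terms related to respiratory function disorders are aspiration, diaphragmatic paralysis, dyspnoea, pneumonia aspiration, respiratory arrest, respiratory depression, and respiratory failure". Six swallowing terms follow.

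**Stopping the study (Protocol 7.5.2).** The same two lists are repeated. Severe events on them that are related to treatment and last more than one week count towards a threshold of five in the first 50 subjects injected, and of 10% of treated subjects after that.

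**Analysis (SAP 6.5.2 and 7.5, Table 4).** A secondary safety variable is "Occurrence of treatment emergent AESIs (TEAESIs) overall and by injection cycle", with AESIs identified by the preferred terms of SAP Table 4.

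**The concern.** Four rules are meant to act on the same class of events: re-injection, expedited reporting, study stopping and AESI analysis. The re-injection rule names a condition that the lists behind the other rules do not contain. If a site writes respiratory distress and the coded term is not a listed one, the event is an AESI by the wording of 7.4 and not an AESI by 10.3.

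Breathing problems are among the main hazards of toxin injected near the pharynx in children, and 7.4 singles this condition out. At stake are prompt AESI reporting, completeness of the AESI tables, and the count that can end the study. Primary efficacy is not touched.

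**Working it through.** No sample size or power figure is involved. The check is a term-by-term comparison, ignoring differences of spelling and punctuation.

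**1. The conditions named in 7.4 criterion 2, looked up in the four lists**

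| Condition | Table 7 | 7.5.1 | 7.5.2 | SAP Table 4 |
|---|---|---|---|---|
| Respiratory arrest | yes | yes | yes | yes |
| Respiratory failure | yes | yes | yes | yes |
| Dysphagia | yes | yes | yes | yes |
| Respiratory distress | no | no | no | no |

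The first three conditions fill 3 × 4 = 12 of 12 cells. Respiratory distress fills 0 of 4.

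**2. Whether the lists are otherwise matched**

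- Table 7 has 49 terms and SAP Table 4 has 49.
- Sections 7.5.1 and 7.5.2 each use 7 respiratory + 6 swallowing = 13 terms. All 13 are in Table 7 and all 13 are in SAP Table 4.
- The two tables differ in four entries, none of them respiratory. Flaccid paralysis and VIIth nerve paralysis are only in Table 7. Facial paralysis and qualified dry mouth are only in SAP Table 4, and 10.3 adds the dry mouth item in text.

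The lists in 7.5.1 and 7.5.2 are subsets of Table 7, and SAP Table 4 largely restates it. The four absences are therefore one omission carried through, not four separate ones.

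**3. What happens to an event recorded and coded only as respiratory distress**

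| Rule | Does it catch the event? |
|---|---|
| 24-hour AESI report (10.3) | No. The 24-hour SAE report applies if the event is serious (10.2). |
| TEAESI tables and listings (SAP 7.5) | No |
| Stopping count (7.5.2) | No, even if severe, related and longer than one week |
| Withdrawal for a severe respiratory AESI (7.5.1) | No |
| Re-injection bar (7.4) | Yes if severe and related, because the condition is named there |
| Withdrawal for unmet re-injection criteria (7.5.1) | Yes, as a result of the 7.4 bar |
| AE recording and TEAE tables | Yes |
| Review by the data monitoring committee (12.4.7.3) | Yes |

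**4. Effect on the stopping count, as an illustration only**

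The threshold is 5 events in the first 50 subjects (5/50 = 10%, in line with the later percentage). Let *k* be the number of otherwise qualifying events recorded only as respiratory distress. Of five true events, 5 − *k* are counted, and 5 + *k* true events are needed to reach the threshold.

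| *k* (assumed) | Counted out of 5 | True events needed |
|---|---|---|
| 0 | 5, threshold met | 5 |
| 1 | 4, not met | 6 |
| 2 | 3, not met | 7 |

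The documents give no rate from which to choose *k*, and *k* = 0 is quite possible.

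**The case against.** The best counter-argument is that two kinds of text are being compared. Table 7 and SAP Table 4 list coded preferred terms, while criterion 2 of 7.4 is clinical prose in which distress, written between slashes, may be bedside shorthand for dyspnea or respiratory failure. Both of those are listed. This reading is plausible, but neither document states it. If it is what was meant, one sentence would settle it.

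The second argument is that the gap is narrow, and this stands. The event must be recorded only as distress, must not code to a listed term, and must not be serious. By 10.1.1 a severe event is incapacitating, and under 10.2 many such events would qualify as serious and be reported within 24 hours anyway. The stopping count further requires relatedness and more than a week's duration. How such an event would be coded cannot be settled from the documents.

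Two stronger readings should be resisted.

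- A reader might infer that the event drops out of safety reporting altogether. It does not: it stays in the AE data, the TEAE tables and committee review, and only the AESI tables and listings miss it.
- A reader might infer that a child with severe, related respiratory distress could be injected again. On the natural reading of 7.4 that child is barred, and failing 7.4 is itself a withdrawal reason in 7.5.1. Section 7.5.1 also requires withdrawal for "Any AE for which treatment continuation would constitute an unacceptably high risk for the subject". A strict reader could argue that 7.4 covers only events that 10.3 defines as AESIs, but that would empty the word distress of meaning.

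Nor is the sponsor confined to the 7.5.2 count: "Reasons for termination of the study or closure of a study site may include, but are not limited to, the following".

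**Conclusion.** The inconsistency is real and visible in the text: one of the four conditions named in criterion 2 of 7.4 is missing from the closed AESI list and from the three lists that follow it. The consequence is conditional. A non-serious event recorded and coded only as respiratory distress falls outside 24-hour AESI reporting, the TEAESI tables and listings, and the 7.5.2 count. The general safeguards remain, but none of them places such an event in those three.

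The number of events affected cannot be derived from the documents and may be zero. The conclusion assumes that the lists are applied literally and that no coding convention outside these documents maps the term to a listed one. Severity is minor.

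**What to change.** Either of two changes would do.

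- **Handling sentence.** State in Protocol 10.3 and in SAP 7.5 that events reported as respiratory distress are handled as a respiratory AESI, and that this holds for 7.5.1 and 7.5.2 as well. This works whether or not the phrase is a suitable preferred term.
- **Add the term.** Put respiratory distress in Table 7, in the respiratory lists of 7.5.1 and 7.5.2, and in SAP Table 4.

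Replacing the word in 7.4 with a listed term would make the sections agree, but would still leave open how an event reported as respiratory distress is handled.

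The cost is one sentence in two documents, or one term in four lists, with no new data collection. The downside is slightly more 24-hour reports and AESI counts, and a marginally more sensitive stopping rule. Severe respiratory distress would also lead to withdrawal even when unrelated, because the severe-AESI rule in 7.5.1 does not ask for relatedness. That already applies to dyspnoea.

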### Table 7: List of AESIs

In addition to the terms listed in Table 7, adverse event 'dry mouth' considered to be severe, serious or irreversible are also to be reported as AESIs.

### 10.4 Expected adverse events

Expected AEs are those listed in the current version of the Investigator's Brochure [IB] for Xeomin®. It should be noted that intraglandular application of BoNT is not necessarily expected to lead to the same adverse events as application at other sites (e.g. intramuscular injection).

#### 10.5 Unexpected adverse events

An unexpected AE is an experience not previously reported in nature, severity, or incidence in the current IB.

## 10.6 Pregnancy

Any pregnancy that starts during the study must be reported by the investigator to the CRO (see contact details in Section 10.2.) within 24 hours of learning of its occurrence. The pregnancy plan will include:

- Ensuring that the young person is treated with respect and confidentiality.
- Measures taken at site to ensure the physical and mental safety and well-being of the mother and baby; the mother will be referred for counseling as appropriate.
- The subject will be withdrawn from the study immediately (apart from end-of-study safety checks and assessments).
- She will receive no further study drug.
- Pregnancies and pregnancy follow-up are to be reported on a pregnancy monitoring form.
- With the explicit consent from the subject's parents or legal representative(s), which must be documented in the subject's medical records, pregnancy follow-up must describe the outcome of the pregnancy, including any voluntary or spontaneous discontinuation; details of the birth; the presence or absence of any congenital abnormalities, birth defects, maternal or newborn complications, and their relation to the IP.

Each pregnancy is to be reported as a non-serious AE (drug exposure before or during pregnancy) within 24 hours of knowledge as well.

